5.1.4 Surgical protocol

Treatment consists of wide local excision of the vulvar tumour or a vulvectomy in combination with SLN procedure. All groins with a SLN on imaging should be explored; also when previously IFL was performed at that site. When sentinel nodes in one or two groins cannot be identified an inguinofemoral lymphadenectomy at either one or two sides should be performed, depending on the location of the tumour and consent of the patient. (Figures 2, 3 and 4) When preoperative imaging showed any enlarged groin node (shortest axis > 8 mm) this node should be removed.

5.1.5 Histopathology:

Macroscopy: the number of lymph nodes received should be described, as well as the size and macroscopic aspects of the lymph nodes. The lymph node should be cut in 2-3 mm slices, perpendicular to the long axis and then all slices should be embedded (do not embed different lymph nodes in the same block).

Microscopy: one routine H/E section (four mu) should be cut of all blocks and two unstained sections (do not cut deep into the block). If the sections are tumour negative step sections, 3 levels/mm (one section per 500 micro meter), should be cut. For the three sections at each level, one is stained with H/E, one is to be used for immunohistochemistry (cytokeratin AE1/AE3), while one spare section is preserved in case of technical difficulties with the IHC (include the first level for IHC). Metastases are defined as clusters of tumour cells of any size detected on haematoxylin and eosin slides or at immunohistochemistry, or isolated tumour cells detected at immunohistochemistry. Anucleate keratin-positive structures are not considered positive. The diameter of the sentinel node metastasis and presence of extranodal growth will be recorded.

Pathologic ultra-staging will only be performed on sentinel nodes and not on non-sentinel nodes as identified in full lymphadenectomy specimens.

Reporting: number of sentinel nodes. Number of lymph nodes in lymphadenectomy specimen. Number of nodes with metastatic involvement. Size of lymph node metastasis. Extra nodal tumour growth.

5.1.6 Additional surgery:

In case of a positive SLN on histology a full IFL is advised. However, local protocol might advise postoperative radiotherapy under certain circumstances.

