5.1.7 Radiotherapy protocol

Standard (chemo) radiotherapy (see www.oncoline.nl for current standard treatment) is indicated postoperatively in case of more than 1 lymph node metastasis or in case of extracapsular tumour growth. Radiotherapy will include the inguinal and low pelvic lymph nodes. Radiotherapy should be initiated within 6 weeks after the final surgical procedure.

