8.1.2 Secondary study parameters/endpoints

Feasibility of the SLN procedure in recurrent vulvar cancer

This is the success rate of detection and retrieval of the sentinel node, both related to the percentage of women, as well as groins in whom the proposed SLN surgery is successfully performed.

Perioperative and postoperative morbidity and mortality

Data collection at 6 weeks after every surgery by the physician. Type of surgery (SLN right groin, SLN left groin, IFL right, IFL left, vulva surgery, reconstructive surgery). Location of SLN found (within IFL region or not), surgical challenges (unintended lesion of vena saphena magna, bleeding, others), duration of surgical procedure, complications (wound infections, wound breakdown, lymph oedema (see adverse effect Appendix 1)), length of hospital stay, re-surgery, readmission.

Incidence of tumour positive sentinel nodes

All specimen will be examined according to the protocol (See section 5.1.) depth of tumour infiltration, presence of LVSI, number of SLN's per groin, number of removed nodes per groin.

Adjuvant treatment

Adjuvant groin treatment; IFL, and or radiotherapy.

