Total number of groins with tumour positive SLNs, divided by the number of groins with successful SLN procedure * 100%.

Tumour positive groins

- in relation to participants / patients with groin surgery (pathology only):

Total number of women with uni or bilateral tumour positive lymph nodes, retrieved either by SLN or by IFL, divided by the number of women that underwent groin surgery * 100% (including women included in the non-SLN cohort, excluding women that did not have groin surgery in groups B2 C).

- in relation to participants / patients with first vulvar cancer recurrence:

Total number of women with uni or bilateral tumour positive lymph nodes, retrieved either by SLN or by IFL, and all women experiencing a groin recurrence during 24 month follow up, divided by the number of women included in the current study * 100% (including women included in the non-SLN cohort, and women that did not have groin surgery in group B2 and C).

- per groin:

Total number of tumour positive nodes divided by the number of groins treated *100%.

Outcome quality of life

QoL measurements will be done at baseline and 6, and 12 months after surgery.

Linear description and comparison between standard treated and study arm treated patients will be performed. (Groups non SLN cohort, and A - C)

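### The per-groin rate of tumour-positive groins (Protocol 10.2) divides positive nodes by groins, so it is not a proportion of groins and overstates per-groin positivity whenever a groin holds more than one positive node

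*Protocol*

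**What the plan says.** Protocol section 10.2 defines three measures under *Tumour positive groins*. Two are per patient, and the first of these is "Total number of women with uni or bilateral tumour positive lymph nodes, retrieved either by SLN or by IFL, divided by the number of women" who had groin surgery. The third, labelled as per groin, is "Total number of tumour positive nodes divided by the number of groins treated *100", expressed as a percentage.

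The block directly above, *Tumour positive SLN's*, also has a per-groin line: "Total number of groins with tumour positive SLNs, divided by the number of groins with successful SLN procedure * 100", again as a percentage.

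Elsewhere the protocol treats nodes as countable items, with several possible per groin. Section 8.1.2 collects "number of SLN's per groin, number of removed nodes per groin". The histopathology section (5.1.5) asks for "Number of nodes with metastatic involvement". Section 5.1.7 sets out radiotherapy "in case of more than 1 lymph node metastasis or in case of extracapsular tumour growth".

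**The concern.** The heading and label announce a percentage of groins, but the formula counts nodes. A groin with three positive nodes adds three to the numerator and one to the denominator. Followed literally, the formula reports a per-groin rate of nodal disease that is too high as soon as one groin holds two or more positive nodes.

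The number would be published as a percentage beside other percentages that are true proportions, and a reader would have no way to see that it is on a different scale. It would also move with the number of positive nodes found in each groin, so it mixes how often groins are involved with how heavily they are involved.

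**Working it through.** The protocol states no value for this rate, so there is no figure to reproduce. The check is algebra, small examples and a comparison with the parallel formulas.

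**Algebra.** Let G be the groins treated, P the groins with at least one positive node, and m the mean number of positive nodes per positive groin. Every positive groin has at least one positive node, so m ≥ 1. The total number of positive nodes is P × m.

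- Protocol formula: (P × m) / G × 100
- Per-groin positivity: P / G × 100
- Ratio of the two: m

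The overstatement is never negative. It is zero only when m = 1.

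**Small examples.**

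- Ten treated groins, two positive with 1 and 3 positive nodes. Protocol formula: 4 / 10 = 40%. Groins: 2 / 10 = 20%.
- Four treated groins, two positive with 1 and 4 positive nodes. Protocol formula: 5 / 4 = 125%. Groins: 2 / 4 = 50%.

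The second example shows that the result is not bounded by 100%.

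**Illustrative size.** The documents do not give m. Take an illustrative true rate of 15 positive groins per 100 treated, and assume values of m:

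- m = 1.0: 15 × 1.0 = 15%
- m = 1.5: 15 × 1.5 = 22.5%
- m = 2.0: 15 × 2.0 = 30%
- m = 2.5: 15 × 2.5 = 37.5%

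Both the 15% and the range of m are assumptions.

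**Slip or choice?** Three features of section 10.2 point to a slip:

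- The per-groin line for tumour-positive SLNs has groins in both numerator and denominator.
- The per-groin feasibility line also has groins over groins.
- The per-patient lines under *Tumour positive groins* count each woman once, whether one or both groins are involved.

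Nothing in the protocol redefines the line as a mean node count.

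**A second line of the same kind.** Also in section 10.2, the measure for SLNs found at unpredicted places divides a number of SLNs by the number of groins treated and expresses it as a percentage. The same mismatch of units arises there.

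**The case against.** The best defence is that the line was meant as a mean number of positive nodes per groin. That reading does not fit the heading, the multiplication to a percentage or the sentinel-node formula above it.

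A stronger defence concerns impact, and much of it stands. The frequency of nodal disease is already given correctly per woman under the same heading, and per woman and per groin for sentinel nodes. No hypothesis, sample size or stopping boundary uses the faulty line. Section 10.3 does not list tumour-positive groins among the outcomes it names for univariate and multivariate modelling.

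Several stronger readings are tempting, and the documents do not support them:

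- *That the protocol calls this quantity poorly known.* What it describes as lacking is information on groin recurrence, procedure failure and outcome of treatment (Summary, 4.4, 13.2). For groin metastases at first local recurrence it gives 18%, from a retrospective study of 200 women (section 1, reused in 4.4).
- *That the 14.5% in section 4.4 can serve as the per-groin base rate.* That figure is per woman undergoing an SLN procedure, not per groin.
- *That the error spoils a planned comparison with the SLN per-groin rate.* No such comparison is planned. Correcting the formula would not make one clean either: only sentinel nodes are ultra-staged (5.1.5), and the non-SLN cohort takes in women whose metastases were found before surgery (4.4, 13.2).
- *That the inflation is known to be largest in groins treated by IFL.* A full dissection can yield more positive nodes per groin than sentinel-node removal, but the protocol gives no node counts by procedure.

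That a separate statistical analysis plan may exist does not settle the matter. The formula is stated, not left open. A plan that follows it repeats the error, and one that departs from it conflicts with the protocol.

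**Conclusion.** The point holds as a definite but contained error. As written, the measure is not a proportion of groins, and it overstates per-groin positivity by the factor m. The direction follows from the algebra and needs no assumption beyond at least one groin holding two or more positive nodes. The protocol foresees more than one node metastasis, although section 5.1.7 does not say within one groin. The size is not documented, so the 22.5% to 37.5% shown for a true 15% is only an illustration.

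The consequence is confined to one descriptive secondary measure. The primary endpoint counts women with a groin recurrence after a negative SLN procedure. That endpoint, the sample size of 150 and the stopping rule are all untouched.

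**What to change.** In section 10.2, under *Tumour positive groins*, per groin, replace the numerator with the total number of groins with at least one tumour-positive node (retrieved by SLN procedure or IFL). State the denominator as the number of groins treated surgically. That wording makes explicit that only groins with pathology can enter, in line with the restriction to groin surgery in the first per-patient measure. If nodal burden is of interest, report the number of positive nodes per positive groin separately, as a count and not a percentage.

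In the same edit, review the measure for SLNs found at unpredicted places. Either count groins with at least one such SLN, or present it as a number of SLNs per groin without the percentage.

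The cost is one or two lines of protocol wording. No new data should be needed. The SLN per-groin formula already requires positivity by groin, and original pathology reports are collected with Form H (Appendix 4). Sections 5.1.5 and 8.1.2 do not explicitly list positive status by groin for IFL specimens, so it is worth confirming that Form H records the side of each positive node.

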Nature and extent of the burden and risks associated with participation, benefit and group relatedness: In this study, similar to the current routine, preoperative imaging of chest, abdomen and groins is performed. The patient is informed about the standard procedure and about the option of a SLN procedure. She and her treating gynaecologist decide on the preferred treatment. Prior to surgery the planned surgical procedure is recorded, including patients' consent for IFL in case the SLN procedure fails. The surgical procedure (SLN procedure) will be less extensive compared to routine IFL, with less unfavourable short and long term effects, such as infections and lymph oedema. In case of groin metastases detected in the SLN procedure further treatment is warranted, either by surgery (uni or bilateral IFL) and/or by radiotherapy. At follow up participants will undergo (non-invasive) ultrasonography studies of the groin at 6 and 12 months. Participants will be asked to fill in additional questionnaires at baseline, 6 and 12 months. In case of a groin recurrence (due to failed SLN procedure) further treatment is warranted, probably resulting in a poorer prognosis with a high mortality rate (probably 80-90%). Currently, robust data on the occurrence of groin recurrence after either SLN biopsy or IFL for recurrent vulvar cancer is lacking. Given the lower morbidity and less short and long term side effects of the SLN procedure compared to IFL an additional 5% failure rate is considered acceptable.

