3. STUDY DESIGN

Preferably a randomized clinical trial or a non-inferiority study should be performed to answer the questions of this study. Given the low incidence of vulvar cancer and the even lower incidence of recurrent vulvar cancer it is not feasible to perform a study other than a multicentre cohort study.

In the participating centres all patients older than 18 years, fit for surgical treatment, with a first vulvar cancer recurrence will be registered.

Standard imaging (i.e., chest, abdominal and groin CT scanning) is performed.

In the absence of distant or proven groin metastases, and when all other eligibility criteria (see Figure 1) are met, the study is proposed and discussed with the patient.

Patients will be informed by oral and written information about the standard treatment (i.e. IFL) and the SLN procedure as part of the study. Patients will be informed that it is possible that the SLN is not traced after injection or at surgery. They will be informed that, should this be the case, standard treatment should be uni- or bilateral IFL. However, from our retrospective study it has become obvious that not all patients will consent for groin treatment and particularly IFL. So three patient groups are identified in *the SLN cohort*. (Figure 1)

- A) Control group: patients who understand the study and choose the standard IFL treatment of the groin(s): These patients will be asked to participate in the conventional treatment arm, with similar questionnaires and follow up.
- B) Patients understanding the study and are willing to undergo a SLN procedure rather than IFL.
 - B1) Patients who agree on IFL(s) in case the SLN is not visible on the lymph scintigram, or not detected at surgery
 - B2) Patients who not agree on IFL(s) in case the SLN is not visible on the lymph scintigram, or not detected at surgery
- C) Patients who agree on vulvar surgery, but refuse any groin surgery. These patients will be asked consent to collect information regarding treatment and outcome, and to fill in the questionnaires.

After surgery *regular follow up* is planned, with visits at 3, 6, 9, 12, 15, 18, 21 and 24 months. For study purposes ultrasonography of the groins is performed at 6 and 12 months. At baseline, at 6 and 12 months QoL questionnaire and a lymph oedema query are requested (see 4.1.3. for questionnaires).

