All women with a first vulvar recurrence not eligible for the SLN procedure, unless not capable to read Dutch or English, will be asked to participate in the observational arm of *the non- SLN cohort*. For this purpose a different patient information folder and different consent forms are applicable. They will receive standard (personalised) treatment and follow up. They will be requested to fill in questionnaires at baseline, 6 and 12 months and if they agree on storage and use of any tumour tissues.

[figure not shown]

Figure 1 Flow diagram of patients with a 1st recurrence of vulvar SCC

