4. STUDY POPULATION

4.1 Population

In the Netherlands vulvar cancer treatment is centralised in university hospitals and cancer clinics. The annual incidence is rising due to the aging population and due to the increase in HPV related vulvar cancer.[www.iknl.nl] A local recurrence occurs in 20-40% of the women.(13) Although IFL is the standard treatment in local recurrent vulvar cancer, more and more clinics perform a SLN procedure, without data on feasibility and safety. Therefore the willingness of the gynaecologic oncologists to participate in this study is high. However, previous national studies (GROINSS-V and GROINS-VII) have shown that a study like this will take a lot of time. We expect that the willingness of patients to participate in this study will be 80% or above, since they can opt for standard treatment or study treatment rather than being randomized.

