4.3 Exclusion criteria

A potential subject who meets any of the following criteria should not undergo the SLN procedure in the study arm (A-B), the patient can be asked for the non SLN cohort.

- Inoperable tumours and tumours with diameter > 4 cm.
- Patients with inguinofemoral lymph nodes at palpation clinically suspect for metastases, at radiology enlarged (> 10 mm short axis) / suspicious groin nodes and with cytological proven inguinofemoral lymph node metastases.
- A history of bilateral IFL **and** radiotherapy to the groins.
- A lateral tumour and history of ipsilateral IFL **and** ipsilateral radiotherapy.
- Tumour encroaching urethra, vagina, or anus.
- Previous surgery of the vulva was not radical (margin < 1 mm) and additional treatment (2nd surgery or radiotherapy) was not performed.
- Multifocal recurrent disease of the vulva.
- Synchronous, non- curable 2nd malignancy.

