4.4 Sample size calculation

Approximately 18% of women will have groin metastases at the moment of their first vulvar cancer recurrence. Of these, approximately 20% will be detected prior to surgery (based on imaging and FNA) and these women will not be offered a SLN procedure, but advised to undergo an IFL(s). They will be asked for the observational arm of the non SLN cohort. (See figure 2)

The remaining patients will be informed about the study, they can decide on standard IFL (group A) or refuse any surgery of the groin(s) (group C) In 75% of cases that undergo SLN (group B) it will be possible to retrieve the SLN. In approximately 14,5% of women undergoing a SLN procedure a tumour positive node will be present. It is not expected that the change of a successful SLN procedure relates to the presence or absence of a positive groin node. We expect to find a positive SLN in 11% of cases undergoing a SLN procedure, a negative SLN in 64%, and an unsuccessful procedure in 25%. This corresponds to respectively 10.5%, 61.8% and 24.1% of all included patients.

Percentage failure of SLN or IFL is known for neither procedure in the recurrent setting. In the primary setting groin recurrence after negative IFL and after negative SLN are both about 3%.

Sample size for V2SLN is calculated based on a conservatively estimated groin recurrence rate of 3%, with a maximum additional groin failure rate of SLN in local recurrent vulvar SCC of 5%. The sample size, considering an alpha of 0.10 and a beta of 0.20, is then calculated to be 150 patients with a first vulvar cancer recurrence undergoing a SLN procedure (group B) and a negative SLN (Figure 2) So, we expect that approximately 243 women with a 1st recurrence of vulvar cancer should be included in the study. Stopping rules with dynamic boundaries were constructed to guarantee the safety of the study by continuously monitoring the number of groin recurrences. See Appendix 1 for a detailed description of these stopping rules.

[figure not shown]

Figure 2 Flow diagram of calculation of sample size

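### The quality-of-life comparison includes women ineligible for SLN and women without groin surgery, so on its natural reading it mixes treatment effect with disease extent and previous groin treatment

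*Protocol*

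**What the plan says.** Protocol section 10.2, under quality of life, sets the schedule, "QoL measurements will be done at baseline and 6, and 12 months after surgery", and then the analysis: "Linear description and comparison between standard treated and study arm treated patients will be performed. (Groups non SLN cohort, and A - C".

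The groups are defined elsewhere in the protocol:

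- **Allocation.** Treatment is chosen. The Summary says "She and her treating gynaecologist decide on the preferred treatment", and section 4.1 expects good participation "since they can opt for standard treatment or study treatment rather than being randomized".
- **Non-SLN cohort.** Section 3 describes it as "All women with a first vulvar recurrence not eligible for the SLN procedure" (apart from those unable to read the study languages) and says these women get standard, individualised treatment. The reasons for ineligibility in section 4.3 begin with "Inoperable tumours and tumours with diameter > 4 cm". They go on to suspicious or proven groin nodes, encroachment on urethra, vagina or anus, multifocal disease, a non-curable second malignancy, and previous IFL combined with groin radiotherapy.
- **Group A.** SLN-eligible women who choose IFL. Section 3 labels them the control group.
- **Group B.** SLN-eligible women who choose the SLN procedure.
- **Group C.** "Patients who agree on vulvar surgery, but refuse any groin surgery".

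Appendix 6 gives the EQ-5D-5L and the adjusted GCLQ to all of these groups at all three time points. Section 10 describes baseline data and tests them for differences between groups. Section 10.3 plans univariate and multivariate analyses for a bracketed list of outcomes: failure of the two procedures, feasibility, unexpected nodes, preferences and ultrasound. Quality of life is not on that list, and no baseline score is among the covariates.

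**The concern.** A comparison of standard-treated with study-treated women is informative about the groin procedure only if the two sides could have received either procedure. The non-SLN cohort could not. Its members were excluded for features that can lower quality of life or raise lymphoedema scores whatever is done to the groin at recurrence. If they count as standard treated, their worse scores would be read as harm from IFL.

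This matters because the Summary accepts an additional 5% groin failure rate on the ground that SLN causes less morbidity than IFL. The EQ-5D and GCLQ contrasts are part of the evidence on that trade-off in recurrent disease. A bias towards SLN would overstate the benefit against which the extra failures are weighed.

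**Working it through.** **1. What the protocol quantifies.** No effect size, SD, correlation, group size or power is given for quality of life, so there is no planned figure to reproduce for this outcome. The only relevant numbers are the patient-flow figures in section 4.4.

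- Groin metastases at first recurrence: 18%. "Of these, approximately 20% will be detected prior to surgery (based on imaging and FNA"; these women go to the non-SLN cohort.
- Share sent to the non-SLN cohort by this route: 0.18 × 0.20 = 0.036, or 3.6%. Of 243 women that is 0.036 × 243 = 8.7, about 9.
- Remaining share: 100 − 3.6 = 96.4%. The flow allots 10.5 + 61.8 + 24.1 = 96.4% to positive, negative and unsuccessful SLN procedures.
- Total: 150 / 0.618 = 242.7, matching the stated 243.

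Two things follow. The other routes into the non-SLN cohort (tumour size, multifocality, encroachment, previous treatment) have no number, so its size is unknown. And the flow assigns everyone else to group B, leaving no women for groups A or C.

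**2. How each group fits the two sides of the comparison.**

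| Group | SLN-eligible | Groin treatment at recurrence | Side |
|---|---|---|---|
| Non-SLN cohort | No | Standard, individualised | Standard, on the natural reading |
| A | Yes | IFL by choice | Standard |
| B | Yes | SLN by choice | Study |
| C | Yes | None | Neither |

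**3. Direction.** Larger or node-positive disease, and the radiotherapy that section 5.1.7 attaches to more than one nodal metastasis or extracapsular growth, would tend to worsen scores on the standard side. The GCLQ is especially exposed. Section 1 cites lymphoedema in 25.2% after IFL and 1.9% after SLN in primary disease, and previous IFL with radiotherapy is itself a route into the non-SLN cohort. Such women may bring lymphoedema from their first treatment. By section 5.1.2, standard care after a previous IFL omits groin surgery, so their scores may say nothing about IFL at recurrence. The likely net direction favours SLN. It is not certain: group C, if placed on the standard side, could pull lymphoedema scores the other way.

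**4. What the baseline score could contribute (assumed inputs).** Let r be the correlation between baseline and follow-up, and d the baseline difference between groups in SD units.

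- Bias left in an unadjusted follow-up difference = r × d.
- Residual variance with baseline as covariate, relative to without = 1 − r²; relative SE = √(1 − r²).

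| r | Bias, d = 0.2 | Bias, d = 0.5 | Residual variance | Relative SE |
|---|---|---|---|---|
| 0.4 | 0.08 | 0.20 | 0.84 | 0.92 |
| 0.5 | 0.10 | 0.25 | 0.75 | 0.87 |
| 0.7 | 0.14 | 0.35 | 0.51 | 0.71 |

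The variance column is the most that can be gained. Where baseline differs between self-selected groups, the covariate is correlated with group and some of the gain is lost.

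**5. What a restricted contrast could detect (assumed group sizes).** For a 0.5 SD difference, two-sided 0.05, 200 women in B and no adjustment, power is 0.57 with 20 women in A, 0.72 with 30 and 0.89 with 50.

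**The case against.** The strongest reply is that pooling is not stated outright. Section 3 calls group A the control group and section 10.2 elsewhere equates the standard arm with group A, so standard treated could mean A alone. The bracketed group list could then merely name who contributes data, as similar brackets do elsewhere in section 10. Secondary objective 3 gives a good reason to describe quality of life in ineligible women. This stands in part: pooling is the natural reading, given what section 3 says about the non-SLN cohort's treatment, but not the only one.

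Second, a reader might infer that the baseline score is collected and then discarded, with a definite loss of precision. The protocol does not support that. It names no model, the word linear beside three time points is undefined and could mean a linear model including baseline, and the detail may sit in a SAP that is not shown. What can be said is that no use of the score is specified.

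Third, self-selection is an openly acknowledged limit of the design, not an analysis error, and A versus B is self-selected too. That is correct. The avoidable part is adding ineligible women, who differ by definition, to a contrast that is already observational.

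Fourth, group A may be too small to serve as comparator. This also stands, and it is a real cost of the fix.

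**Conclusion.** The point holds in a limited form. The sentence in section 10.2 puts the SLN-ineligible cohort and group C into a comparison of standard with study treatment. On its natural reading this confounds groin treatment with disease extent and previous groin treatment, probably to the advantage of SLN. Quality of life is outside the only covariate plan in the protocol, and no role is given to the baseline score.

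The size of the distortion cannot be derived from the protocol. The biases of 0.08 to 0.35 SD shown above rest on assumed correlations and imbalances. They concern only the part that a baseline score could remove; adjusting for that score would not make ineligible women comparable with eligible ones. Any precision gain is likewise conditional on an unstated correlation. The outcome is secondary and has no decision rule, so the consequence is for the interpretation of the quality-of-life and lymphoedema contrasts. The primary endpoint is unaffected.

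**What to change.** Reword the quality-of-life paragraph in section 10.2 so that:

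- the treatment contrast for EQ-5D-5L and GCLQ is group B versus group A, with groups as section 3 defines them, at 6 and 12 months;
- it is adjusted for the baseline score and, as numbers allow, for age and previous groin treatment;
- the non-SLN cohort and group C are each described separately, which serves secondary objective 3;
- the contrast is presented as observational.

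All the data are already to be collected, so the change is to wording only. The price is a smaller IFL comparator. Section 10.2 makes even the groin-recurrence analysis in group A depend on enough women choosing IFL, and the section 4.4 flow allows for none. The contrast may therefore be imprecise, or only descriptive if group A is very small, and the plan should say so in advance. Differences between women who choose IFL and women who choose SLN will remain beyond what the covariates capture.
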